9.1.3. Analysis of Safety

Analysis of safety data will be presented for all subjects in the Safety population (i.e., all subjects receiving randomized study product). AEs will be coded using Medical Dictionary for Regulatory Activities (MedDRA, most current version) and categorized by system organ class using preferred terms. AEs will be tabulated by study group with respect to their intensity and relationship to the study product. Ophthalmoscopy findings will be summarized descriptively. IOP measurements, Snellen Distance VA by pinhole method and Slit Lamp Biomicroscopy will be summarized as safety outcomes.

9.2. SAMPLE SIZE ESTIMATION

A two group χ^2 test with a 0.05 two-sided significance level will have 99% power to detect the difference between a proportion with complete resolution of anterior chamber cells in the active group of 0.31 and the placebo group proportion of 0.15 when the sample size in each group is 250. The power is the same for the complete resolution of pain endpoint.

9.3. LEVEL OF SIGNIFICANCE

The primary assessment will be evaluated using a 5% level of significance using the hierarchical testing described in Section 9.1.2 Analysis of Efficacy.

All other reported p-values will be considered descriptive and hypothesis generating.

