Secondary Efficacy Endpoints:

- Proportion of study eyes with complete resolution of ocular pain (grade = 0) at Visit 4 (Day 4 ± 1 day) maintained through Visit 6 (Day 15 ± 1 day) without receiving rescue medication prior to Visit 6 (Day 15 ± 1 day) as compared between KPI-121 1.0% ophthalmic suspension dosed BID and placebo dosed BID. This endpoint will be tested at α = 0.0167.
- 2. Proportion of study eyes with complete resolution of anterior chamber flare (grade = 0) at Visit 4 (Day 4 ± 1 day) maintained through Visit 6 (Day 15 ± 1 day) without receiving rescue medication prior to Visit 6 (Day 15 ± 1 day) as compared between KPI-121 1.0% ophthalmic suspension dosed BID and placebo dosed BID. This endpoint will be tested at α = 0.0167.
- 3. Change from baseline in mean anterior chamber cell count at Visit 4 (Day 4 ± 1 day) as compared between KPI-121 1.0% ophthalmic suspension dosed BID and placebo dosed BID. This endpoint will be tested at $\alpha = 0.0167$.

Safety Endpoints

Assessment of AEs

Snellen Distance VA by Pinhole Method

Slit Lamp Biomicroscopy

IOP measurement

Dilated Ophthalmoscopy

Change from baseline to each post-surgery visit in ocular signs:

- Palpebral conjunctival erythema
- Corneal edema
- Hyphema
- Ciliary flush

| Bulbar conjunctival injection | | | |
|-------------------------------|--|--|--|
| Eligibility Criteria: | Inclusion Criteria: | | |
| Eligibility Criteria: | Inclusion Criteria: At Visit 1, individuals of either gender or any race will be eligible for study participation if they: Provide written informed consent and Health Insurance Portability and Accountability Act (HIPAA) authorization prior to any study-related procedures. Are 18 years of age or older. Are willing and able to follow instructions and can be present for the required study visits for the duration of the study. Are candidates for routine, uncomplicated cataract surgery [e.g., phacoemulsification with posterior chamber intraocular lens (IOL) implantation, not combined with any other surgery]. In the Investigator's opinion, have potential postoperative Snellen Distance VA by pinhole method of at least 20/200 in the study eye. Are women of child bearing potential (WOCBP) who are not pregnant or lactating and not sexually active (i.e., abstinent) for 14 days prior to Visit 1 and are willing to remain so through 30 | | |
| | | | |

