3. TRIAL DESIGN

3.1. PRIMARY EFFICACY ENDPOINTS

The primary endpoints of this study will be evaluated using hierarchical statistical testing in the following sequence:

- 1. Proportion of study eyes with complete resolution of anterior chamber cells (grade = 0) at Visit 5 (Day 8 ± 1 day) maintained through Visit 6 (Day 15 ± 1 day) without receiving rescue medication prior to Visit 6 (Day 15 ± 1 day) as compared between KPI-121 1.0% ophthalmic suspension dosed BID and placebo dosed BID.
- 2. Proportion of study eyes with complete resolution of pain (grade = 0) at Visit 5 (Day 8 ± 1 day) maintained through Visit 6 (Day 15 ± 1 day) without receiving rescue medication prior to Visit 6 (Day 15 ± 1 day) as compared between KPI-121 1.0% ophthalmic suspension dosed BID and placebo dosed BID.

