3.2. SECONDARY EFFICACY ENDPOINTS

- Proportion of study eyes with complete resolution of ocular pain (grade = 0) at Visit 4
 (Day 4 ± 1 day) maintained through Visit 6 (Day 15 ± 1 day) without receiving rescue
 medication prior to Visit 6 (Day 15 ± 1 day) as compared between KPI-121 1.0%
 ophthalmic suspension dosed BID and placebo dosed BID. This endpoint will be tested at
 α = 0.0167.
- 2. Proportion of study eyes with complete resolution of anterior chamber flare (grade = 0) at Visit 4 (Day 4 ± 1 day) maintained through Visit 6 (Day 15 ± 1 day) without receiving rescue medication prior to Visit 6 (Day 15 ± 1 day) as compared between KPI-121 1.0% ophthalmic suspension dosed BID and placebo dosed BID. This endpoint will be tested at $\alpha = 0.0167$.
- 3. Change from baseline in mean anterior chamber cell count at Visit 4 (Day 4 ± 1 day) as compared between KPI-121 1.0% ophthalmic suspension dosed BID and placebo dosed BID. This endpoint will be tested at $\alpha = 0.0167$.

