9.1.2. Analysis of Efficacy

The primary analysis population will be the Intent-to-Treat (ITT) population, defined as all subjects randomized. A subset of efficacy analyses will be repeated using data from those subjects who were randomized, completed 14 days of study product use, had complete data at Visit 5 (Day 8 ± 1 day) and did not have significant protocol deviations, the Efficacy Evaluable (EE) population. Rescued subjects will be included in the EE population if they did not have significant protocol deviations.

The primary analysis of all ophthalmic efficacy measures will be based on a single study eye for each subject. Each subject's study eye will be defined as the surgery eye. The set of primary endpoints, using hierarchical statistical testing, is (1) proportion of study eyes with complete resolution of anterior chamber cells (grade = 0) at postoperative Visit 5 (Day 8 ± 1 day) maintained through Visit 6 (Day 15 ± 1 day) without receiving rescue medication prior to Visit 6 (Day 15 ± 1 day) as compared between KPI-121 1.0% ophthalmic suspension and placebo, and (2) proportion of study eyes with complete resolution of pain (grade = 0) at postoperative Visit 5 (Day 8 ± 1 day) maintained through Visit 6 (Day 15 ± 1 day) without receiving rescue medication prior to Visit 6 (Day 15 ± 1 day) as compared between KPI-121 1.0% ophthalmic suspension and placebo.

The following scoring scale for anterior chamber cells will be used:

0 = No cells seen

1 = 1 - 5 cells

2 = 6 - 15 cells

3 = 16 - 30 cells

4 =greater than 30 cells

The following scoring scale for ocular pain will be used:

- 0 = None
- 1 = Minimal
- 2 = Mild
- 3 = Moderate
- 4 = Moderately Severe
- 5 = Severe

Using the hierarchical testing scheme, the first test will be the proportion of study eyes with complete resolution of anterior chamber cells (grade = 0) at Visit 5 (Day 8 ± 1 day) maintained through Visit 6 (Day 15 ± 1 day) without receiving rescue medication prior to Visit 6 (Day 15 ± 1 day) as compared between KPI-121 1.0% ophthalmic suspension dosed BID and placebo dosed BID using the χ^2 statistic.

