If this test is statistically significant at the two-sided $\alpha = 0.05$ level in favor of the KPI-121 1.0% ophthalmic suspension group, then the difference in the proportion of study eyes with complete resolution of pain (grade = 0) at Visit 5 (Day 8 ± 1 day) maintained through Visit 6 (Day 15 ± 1 day) without receiving rescue medication prior to Visit 6 (Day 15 ± 1 day) as compared between KPI-121 1.0% ophthalmic suspension dosed BID and placebo dosed BID will be tested using the same statistic.

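### The three secondary endpoints are given a formal test level of 0.0167 each, but Section 9.3 makes every non-primary p-value descriptive, and no rule ties the secondaries to the primaries

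*Combined protocol and SAP*

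**What the plan says.** - **Secondary endpoints.** The synopsis lists three: pain resolution from Visit 4, flare resolution from Visit 4, and change in anterior chamber cells at Visit 4. To each it attaches the statement "This endpoint will be tested at α = 0.0167". Section 3.2 repeats this ("dosed BID and placebo dosed BID. This endpoint will be tested at", followed by the same 0.0167).
- **Significance level.** Section 9.3 says "The primary assessment will be evaluated using a 5% level of significance using the hierarchical testing described in" Section 9.1.2, and then "All other reported p-values will be considered descriptive and hypothesis generating".
- **Scope of the hierarchy.** Section 3.1 says "The primary endpoints of this study will be evaluated using hierarchical statistical testing in the following sequence" and lists cells, then pain. Section 9.1.2 defines the same two ("The set of primary endpoints, using hierarchical statistical testing, is").
- **The only gate.** Section 9.1.2 opens the Day 8 pain test on the result for cells: "If this test is statistically significant at the two-sided" 0.05 level in favour of KPI-121. No comparable sentence covers the secondaries. Section 9 mentions neither them nor the 0.0167 level.

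**The concern.** A level of 0.05/3 per endpoint has a purpose only if the three results are meant to support formal claims; a descriptive p-value needs no threshold. The synopsis and Section 3.2 therefore imply one status for the secondaries and Section 9.3 states another.

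This bites whether or not the primaries succeed. If both succeed, Section 3.2 permits a formal secondary claim and Section 9.3 rules it out. If the cells primary fails, Section 9.1.2 closes the Day 8 pain test, but nothing closes the Day 4 pain test at 0.0167. An eye free of pain from Visit 4 through Visit 6 is also free of pain from Visit 5 through Visit 6, so Day 4 pain successes are a subset of Day 8 pain successes. On the unconditional reading, the trial could claim the stricter pain endpoint after its hierarchy had barred the broader one.

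As the text stands, the reading could be chosen after the results are known.

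**Working it through.** **Inputs from the documents.** Cells primary: two-sided 0.05 (Section 9.1.2). Secondaries: three at 0.0167 (synopsis, Section 3.2; sidedness not stated, taken here as two-sided). Power assumptions: 0.31 vs 0.15 with 250 per group (Section 9.2). The documents give no correlations between endpoints, so those below are assumed.

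**1. The plan's own figures.**

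- Pooled proportion: (0.31 + 0.15)/2 = 0.23.
- Null SE: √(2 × 0.23 × 0.77/250) = 0.03764. Alternative SE: √((0.31 × 0.69 + 0.15 × 0.85)/250) = 0.03695.
- z = (0.16 − 1.960 × 0.03764)/0.03695 = 2.333, so power = 0.990. The stated 99% reproduces.
- 0.05/3 = 0.01667, which rounds to 0.0167.

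**2. Family-wise error if the secondaries are unconditional (global null).** The Day 8 pain primary is reached only after cells has rejected, so it adds no further chance of a first false positive. Four tests count: cells and the three secondaries.

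- Upper bound: 0.05 + 3 × 0.0167 = 0.1001.
- Independent: 1 − 0.95 × (1 − 0.0167)³ = 0.0968.
- Common correlation ρ: 1 − ∫ φ(u) A(u) B(u)³ du. Here A and B are the probabilities, given the shared factor u, that |√ρ·u + √(1−ρ)·e| stays below 1.960 and 2.393 respectively, with e standard normal.

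**3. False claims in favour of KPI-121 only.** Each level is halved: 0.025 for cells and 0.00835 per secondary. Independent: 1 − 0.975 × (1 − 0.00835)³ = 0.0492. With the secondaries conditional on both primaries, the figure is 0.025. The difference is the chance that a secondary falsely favours KPI-121 when the cells primary has not succeeded.

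| Assumed correlation | Either direction | In favour of KPI-121 | Excess over 2.5% |
|---|---|---|---|
| 0 | 9.7% | 4.9% | 2.4% |
| 0.3 | 9.2% | 4.6% | 2.1% |
| 0.5 | 8.5% | 4.2% | 1.7% |
| 0.7 | 7.3% | 3.7% | 1.2% |
| 0.9 | 5.7% | 2.9% | 0.35% |

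A simulation of 1,000,000 draws gave either-direction values within 0.05 percentage points of the integration at correlations 0.3 to 0.9.

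**4. Conditional or descriptive secondaries.** If they are tested only after both primaries succeed in favour of KPI-121, simulated family-wise error is 0.050 at correlations 0, 0.3, 0.5 and 0.8. If they are descriptive, confirmatory error is 0.05 by construction.

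**5. How often the condition would matter.** Section 9.2 says "The power is the same for the complete resolution of pain endpoint", so each primary has power 0.990. Whatever their correlation, both succeed with probability at least 2 × 0.990 − 1 = 0.980.

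**The case against.** The strongest reply is that Section 9.3 is the section on significance levels and, read literally, gives the secondaries a definite status: descriptive. The 0.0167 levels are then leftovers, and error is not inflated. That is a fair reading, and on it the defect is purely an inconsistency. But it leaves six statements of a test level (three in the synopsis, three in Section 3.2) that have to be removed, and nothing in the text says that Section 9.3 prevails.

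Four further points carry weight:

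- **The inflation is conditional.** It requires both that Section 3.2 overrides Section 9.3 and that silence on gating means no gate. No passage expressly permits a secondary claim after a failed primary. This stands, and the error rates should be read that way.
- **The two-directional figures overstate the practical risk.** They include results favouring placebo. The excess in favour of KPI-121 is the more relevant number. Independence is also implausible for signs and symptoms in the same eye.
- **The subset relation is limited.** It does not make the Day 4 treatment difference smaller than the Day 8 one. It shows only that the order of claims is odd if no gate exists.
- **A separate analysis plan may settle the point.** Section 9.5 refers to one, and it cannot be ruled out that it fixes the status before unmasking. The protocol text would still contradict itself.

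The low chance of a primary failing limits the effect of the missing gate. It does not resolve the conflict, which is present when both primaries succeed.

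**Conclusion.** The concern holds. The synopsis and Section 3.2 contradict Section 9.3 on whether the secondaries are formally tested, and the plan's one gate does not reach them. The contradiction follows from the text alone and needs no assumption.

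The error-rate consequence does need one. Only if Section 3.2 governs without a gate does family-wise error exceed 5%, reaching at most 10.0% in either direction. The excess false claims for KPI-121 then run from about 0.35% to 2.4% across assumed correlations of 0.9 down to 0. These figures rest on the global null, two-sided tests and equal correlations, none of which the documents specify for the secondaries. The primary hierarchy, its 5% level and its 99% power are untouched. This should be fixed, but it does not threaten the trial's main conclusion.

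**What to change.** State one status before unmasking. Two options are sound, and choosing between them is the sponsor's decision:

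- **(a) Formal secondaries.** In the synopsis and Sections 3.2, 9.1.2 and 9.3, say that the three secondaries are tested at 0.0167 each, with sidedness stated, only if both primaries are significant in favour of KPI-121. Exempt them from the last sentence of Section 9.3. Other gating schemes could also control the error; this one keeps the existing levels.
- **(b) Descriptive secondaries.** Delete the 0.0167 levels from the synopsis and Section 3.2 and leave Section 9.3 as it is.

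Either costs a few lines of wording and leaves sample size, visits and data collection unchanged. Under (a), secondary claims are lost if a primary fails, which is at most 2% of the time under the plan's own power assumptions (1 − 0.980). Under (b), no formal secondary claim is possible. If a separate analysis plan already fixes the status, the protocol text should be aligned with it.

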9.4. PROCEDURE FOR ACCOUNTING FOR MISSING, UNUSED, OR SPURIOUS DATA

If more than 5% of data points are missing at the primary analysis time point (Day 8) in any treatment group, a tipping point analysis will be employed to assess the sensitivity of the results to the distribution of the allocation of treatment success and failure to the missing data points.

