5.2. SUBJECT WITHDRAWAL AND/OR DISCONTINUATION

Any subject who wishes to discontinue investigational product use or withdraw from participation in the study for any reason is entitled to do so without obligation. The Investigator may also discontinue any subject from investigational product use or from study participation, if deemed necessary.

Investigational product use may be discontinued and any subject may be discontinued from study participation at any time during the study at the discretion of the Investigator or the sponsor for any reason including but not limited to:

- 1. Occurrence of any medical condition or circumstance that exposes the subject to substantial risk and/or does not allow the subject to adhere to the requirements of the protocol.
- 2. Any SAE, clinically significant AE, severe laboratory abnormality, intercurrent illness, or other medical condition that indicates to the Investigator that continued participation is not in the best interest of the subject.
- 3. Subject's decision to withdraw.
- 4. Any woman who becomes pregnant while participating in the study. Information on the pregnancy and outcome will be requested.
- 5. Subject's failure to comply with protocol requirements or study related procedures.
- 6. Termination of the study by the Sponsor, FDA, or other regulatory authorities.

In the event study discontinuation of a randomized subject is necessary, the Investigator should make every attempt to have the subject complete Visit 6 assessments as possible. If a non-serious AE is unresolved at the time of the subject's final study visit, an effort will be made to follow up until the AE is resolved or stabilized, the subject is lost to follow-up, or there is some other resolution of the event. The Investigator should make every attempt to follow all serious adverse events (SAEs) to resolution. The reason for premature discontinuation should be entered onto the Case Report Form (CRF) and recorded in the subject chart.

Subjects who withdraw from the study will not be replaced.

Additionally, the trial or parts of the trial may be discontinued by the sponsor or at the recommendation of the Investigator after consultation with Kala Pharmaceuticals, Inc. This may be based on a significant number of AEs of a similar nature that warrant such action.

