5.4. RESCUE MEDICATION USE

Any subjects not responding adequately to the study medication may be rescued and placed on alternate therapy at the Investigator's discretion at any time. The choice of rescue medication is at the Investigator's discretion. Any subject placed on rescue therapy will discontinue use of the study medication and continue study participation through Visit 7.

Rescued subjects will be considered treatment failures, but the need for rescue therapy will not be considered an AE. Rescued subjects experiencing an AE at the time of rescue will be followed through stabilization or resolution of the AE or the end of the study (whichever comes last). Rescued subjects should not be withdrawn from the study, but rather followed to resolution of signs and symptoms or until the Investigator has deemed the subject is stable.

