9.5. PROCEDURE FOR REPORTING DEVIATIONS FROM THE STATISTICAL PLAN

Any deviations from the statistical analysis plan will be described and a justification given in the final clinical study report.

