9.6. SUBJECTS TO BE INCLUDED IN THE ANALYSIS

Efficacy analysis will be performed for all randomized subjects, the Intent-to-Treat (ITT) population. A subset of the efficacy analysis will be repeated using data from those subjects who were randomized, completed 14-days of study product use, had complete data at Visit 5 (Day 8 ± 1 day) and did not have significant protocol deviations, the Efficacy Evaluable (EE) population. Rescued subjects will be included in the EE population if they did not have significant protocol deviations. AEs and other safety parameters will be analyzed for all randomized subjects receiving randomized study product (Safety population).

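### The Section 9.4 tipping-point trigger counts only data missing at Day 8, although both primary endpoints also depend on Day 15

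*Combined protocol and SAP*

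**What the plan says.** Section 9.4 requires a tipping-point analysis "If more than 5% of data points are missing at the primary analysis time point (Day 8) in any treatment group". The analysis reallocates success and failure among the missing data points. It is the only missing-data sensitivity analysis in the document.

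Section 3.1 defines both primary endpoints, cells and then pain, by "grade = 0) at Visit 5 (Day 8 ± 1 day) maintained through Visit 6 (Day 15 ± 1 day"), with no rescue before Visit 6. Section 9.1.2 repeats this and states: "The primary analysis population will be the Intent-to-Treat (ITT) population, defined as all subjects randomized".

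Four other places bear on the point:

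- Section 5.4: "Rescued subjects will be considered treatment failures". A rescued eye therefore has a known outcome.
- Section 5.2, on discontinuation: "the Investigator should make every attempt to have the subject complete Visit 6 assessments as possible".
- Sections 9.1.2 and 9.6: the Efficacy Evaluable (EE) set is limited to subjects who "completed 14-days of study product use, had complete data at Visit 5 (Day 8 ± 1 day") and had no significant deviations. No Visit 6 data condition is named.
- Section 9.5: "Any deviations from the statistical analysis plan will be described". This leaves room for a separate SAP. The document contains no rule for scoring a missing Visit 6 value in the ITT test.

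**The concern.** An eye's primary outcome is fixed by Visit 5, Visit 6 and rescue data together. The trigger looks at Visit 5 alone. One group falls between the two: eyes at grade 0 on Day 8, not rescued, with no Day 15 grade. They may be successes or failures, but Section 9.4 treats them as complete. Because the allocation is described for the same missing data points, they could also be left out of the analysis when it does run.

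The group has clear limits. Eyes above grade 0 at either visit and rescued eyes are failures already, and eyes lost by Day 8 are counted. Membership also differs by endpoint, since an eye can be free of cells but not of pain on Day 8.

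What is at stake is whether a positive ITT result could depend on unobserved outcomes in more than 5% of an arm with no sensitivity analysis required.

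**Working it through.** **Inputs from the protocol.** Section 9.2 gives a two-sided 0.05 chi-square test with "active group of 0.31 and the placebo group proportion of 0.15 when the sample size in each group is 250", and 99% power. These rates are for cells. For pain the section says only that power is the same, so the figures below apply to cells.

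**The plan's own figure.** Using the pooled-variance formula, the mean rate is 0.23. The null standard error is √(2 × 0.23 × 0.77/250) = 0.03764. The alternative standard error is √(0.31 × 0.69/250 + 0.15 × 0.85/250) = 0.03695. Power = Φ[(0.16 − 1.96 × 0.03764)/0.03695] = 99.0%. This reproduces the stated value.

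**Trigger.** 5% of 250 is 12.5, so at least 13 eyes in one arm must be missing at Day 8.

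**Assumptions (none of these is in the protocol).**
- Loss is random and equal in the two arms.
- The planned rates hold among completers, and undetermined eyes start as failures.
- The share c of placebo eyes clear and unrescued at Day 8 lies between 0.15 and 0.40. The lower end is implied by the plan, because every placebo success must be clear at Day 8. The upper end is assumed.
- Undetermined placebo eyes = all lost by Day 8 + c × those lost after Day 8.
- Worst case: every undetermined placebo eye is a success and no undetermined active eye is.

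The test is the Pearson chi-square without continuity correction: z = (a − b)/250 ÷ √(2p̄(1 − p̄)/250), where a and b are the active and placebo successes and p̄ = (a + b)/500.

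**1. All loss after Day 8, so the Section 9.4 count is zero**

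| Loss per arm | Observed successes | Undetermined placebo eyes | Worst-case comparison | p |
|---|---|---|---|---|
| 5% | 74 v 36 | 2 to 5 | 74 v 38 to 74 v 41 | 0.0001 to 0.0005 |
| 10% | 70 v 34 | 4 to 10 | 70 v 38 to 70 v 44 | 0.0005 to 0.006 |
| 15% | 66 v 32 | 6 to 15 | 66 v 38 to 66 v 47 | 0.002 to 0.042 |
| 20% | 62 v 30 | 8 to 20 | 62 v 38 to 62 v 50 | 0.007 to 0.20 |

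For example, at 10% loss there are 225 completers: 0.31 × 225 ≈ 70 and 0.15 × 225 ≈ 34. The 25 lost placebo eyes give 0.15 × 25 ≈ 4 to 0.40 × 25 = 10 undetermined.

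**2. 12 per arm (4.8%) lost by Day 8, with more lost afterwards; trigger off throughout**

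| Further loss after Day 8, per arm | Observed successes | Undetermined placebo eyes | Worst-case comparison | p |
|---|---|---|---|---|
| 0 | 74 v 36 | 12 (4.8%) | 74 v 48 | 0.007 |
| 12 (9.6% in total) | 70 v 34 | 14 to 17 (5.6% to 6.8%) | 70 v 48 to 70 v 51 | 0.021 to 0.047 |
| 24 (14.4% in total) | 66 v 32 | 16 to 22 (6.4% to 8.8%) | 66 v 48 to 66 v 54 | 0.055 to 0.21 |

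**3. Late loss alone needed for 13 undetermined eyes (5.2%).** The loss rate is 13/(250c): 34.7% at c = 0.15 and 13.0% at c = 0.40. In the active arm c is at least 0.31 under the plan, so at most 16.8%.

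**4. Smaller observed effects, against 38 placebo successes**

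| Active successes | Undetermined placebo eyes that remove significance | p at that point |
|---|---|---|
| 75 | 18 (7.2%) | 0.053 |
| 70 | 14 (5.6%) | 0.061 (13 eyes: 0.047) |
| 68 | 12 (4.8%) | 0.058 |
| 65 | 9 (3.6%) | 0.054 |

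The last two rows lie below any 5% trigger, however it is defined.

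**The case against.** The best counter-argument is that the affected group is small and the consequences modest. Section 5.1.8 provides an early termination visit that records pain and cell grades. Section 5.3.1 has the Visit 6 forms completed when a subject leaves at an unscheduled visit. Section 5.2 asks for Visit 6 assessments on discontinuation. Many eyes that leave after Day 8 may therefore carry a late grade. The 14-day product-use condition also removes most such eyes from the EE set. On late loss alone, the planned effect tips only somewhere above 15% loss, which is a lot for the week between Visits 5 and 6.

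The figures have limits too. In the second table, 12 of the undetermined eyes come from the 5% threshold itself, and the Day 15 gap adds only 2 to 5 or 4 to 10. The survival at 15% loss depends on the assumed 40% ceiling: one more placebo eye, 66 v 48, gives p = 0.055. A separate SAP might also cover missing data.

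These points narrow the gap without closing it. Nothing says that a grade taken at early termination stands for Day 15, and no safeguard reaches a subject who never returns. The EE analysis repeats a subset of the efficacy analyses in a selected population, so it does not test the ITT result. Reading missing data points as missing endpoint status would resolve the matter, but the parenthesis in Section 9.4 names Day 8.

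**Conclusion.** The concern holds: Section 9.4 as written does not cover the endpoint it is meant to protect. The mismatch follows from the text and does not depend on any assumed loss rate. It is confined to the sensitivity analysis and should be fixed.

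Its practical size does depend on assumptions: 250 per arm, the planned cell rates among completers, equal random loss, and 15% to 40% of placebo eyes clear at Day 8. Under these, late loss alone leaves the planned effect significant through 15% loss and possibly not at 20%. Combined with Day 8 losses just under the threshold, more than 5% of the placebo arm can be undetermined, and significance can be lost in the worst case, with nothing required by Section 9.4. A smaller observed effect would be more fragile, and non-random loss could be worse.

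**What to change.** In Section 9.4, replace the Day 8 count with a count of eyes whose endpoint status cannot be determined from Visit 5, Visit 6 and rescue data. Apply the 5% threshold per arm and per primary endpoint, and allocate success and failure to all such eyes, for cells and for pain. Alternatively, always run the analysis, which also covers effects that tip below 5%.

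As a secondary clarification, state in Section 9.4, or confirm in any separate SAP, that undetermined eyes count as non-responders in the primary ITT test.

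The cost is a few sentences and at most one more sensitivity table per primary endpoint, which would be reported even if unfavourable. If the non-responder rule is adopted, the observed rates fall slightly. With 10% equal loss they become 0.31 × 0.9 = 27.9% and 0.15 × 0.9 = 13.5%, with power about 98%. With 20% loss they become 24.8% and 12.0%, with power about 96%.
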